**Gastrointestinal Toxicity**

**Nausea/Vomiting/Dehydration:** In this protocol, the routine use of any and all anti-emetics is allowed as clinically appropriate; these include the use of dexamethasone and 5-HT3 receptor antagonists.

Patients should maintain adequate fluid and food intake because vorinostat's dose-limiting toxicities are anorexia, dehydration, diarrhea, and fatigue. In the setting of dysgeusia, popsicles and Gatorade have been found to be useful by some investigators to maintain adequate hydration. Patients should also be encouraged to seek a nutritional consult.

**Diarrhea:** Treat diarrhea promptly with appropriate supportive care, including loperamide. Instruct patients to begin taking loperamide at the first signs of 1) poorly formed or loose stool, 2) occurrence of more bowel movements than usual in one day, or 3) unusually high volume of stool. Loperamide should be taken in the following manner: 4 mg at first onset of diarrhea then 2 mg after each unformed stool. The daily dose should not exceed 16 mg. Loperamide should not be taken prophylactically. Advise patients to drink plenty of clear fluids to help prevent dehydration caused by diarrhea. Avoid loperamide if there is the presence of blood or mucus in the stool or if diarrhea is accompanied by fever. If diarrhea is suspected to be linked to pembrolizumab and is ≥ grade 3, hold dose until toxicity resolves to ≤ grade 1, then resume at dose given in prior cycle.

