## **6.6 Prohibited Medications**

Subjects are prohibited from receiving the following therapies during the Screening and Treatment Phase (including retreatment for post-complete response relapse) of this trial:

- Anti-cancer systemic chemotherapy or biological therapy
- Immunotherapy not specified in this protocol
- Chemotherapy not specified in this protocol
- Investigational agents other than Pembrolizumab
- Radiation therapy

- Note: Radiation therapy to a symptomatic solitary lesion or the brain may be allowed after consultation with the study PI and Merck.
- Live vaccines within 30 days prior to the first dose of trial treatment and while participating in the trial. Examples of live vaccines include, but are not limited to, the following: measles, mumps, rubella, chicken pox, yellow fever, rabies, BCG, and typhoid (oral) vaccine. Seasonal influenza vaccines for injection are generally killed virus vaccines and are allowed; however, intranasal influenza vaccines (e.g., Flu-Mist®) are live attenuated vaccines and are not allowed.
- Glucocorticoids for any purpose other than to modulate symptoms from an event of clinical interest of suspected immunologic etiology. The use of physiologic doses of corticosteroids may be approved after consultation with the study PI and Merck.

Subjects who, in the assessment by the investigator, require the use of any of the aforementioned treatments for clinical management should be removed from the trial. Subjects may receive other medications that the investigator deems to be medically necessary.

The Exclusion Criteria describes other medications, which are prohibited in this trial.

There are no prohibited therapies during the Post-Treatment Follow-up Phase.

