### Appendix 3 Prohibited Medications List

---

Drug	Trade name (if applicable)
BCG (Intravesical or vaccine) - ok if on ARM B	Theracys. TICE-BCG
BuPROPion	Wellbutrin
Cladribine - ok if on ARM B	Mavenclad
Conivaptan	Vaprisol
Dacomitinib	Vizimpro
Deferiprone - ok if on ARM B	Ferriprox
Dexamethasone	Prozac
Fludrocortisone	
FLUoxetine	Prozac
Hydrocortisone (topical is okay)	Cortef
Idelalisib	Zydelig
PARoxetine	Paxil
Methylprednisolone	Medrol
Ospemifene	Osphena
Prednisone	Deltisone
Tipranavir	Aptivus
Triamcinolone (topical, inhaled is ok)	Kenalog

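### Section 5.2 permits dexamethasone as a routine anti-emetic, while Section 6.6 and Appendix 3 prohibit it during screening and treatment

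*Combined protocol and SAP*

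**What the plan says.** The paragraph on nausea, vomiting and dehydration in Section 5.2 (Gastrointestinal Toxicity) states that "the routine use of any and all anti-emetics is allowed as clinically appropriate", and continues: "these include the use of dexamethasone and 5-HT3 receptor antagonists". It sets no dose limit, asks for no approval, and does not refer to Section 6.6.

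Section 6.6 lists what subjects may not receive during the Screening and Treatment Phase, retreatment included. One entry is "Glucocorticoids for any purpose other than to modulate symptoms from an event of clinical interest of suspected immunologic etiology". It adds one further exception: "The use of physiologic doses of corticosteroids may be approved after consultation with the study PI and Merck". The section then says that subjects who, in the investigator's assessment, need one of the listed treatments for clinical management should be removed from the trial.

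Appendix 3, the list of prohibited medications, has an entry for "Dexamethasone" with no exemption by arm, route or indication.

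**The concern.** One drug, in one treatment period, is named as allowed in one section and barred in another. Section 5.2 is where a clinician would look for how to manage nausea, and nothing there warns of the prohibition.

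What is at stake is the handling of individual patients. Someone who applies 5.2 treats a dose of dexamethasone as ordinary supportive care. Someone who applies 6.6 sees a barred drug and, if the patient is judged to need it, an instruction to take the patient off the trial. Two patients in the same clinical situation could therefore be handled differently, one kept on study and the other removed.

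**Working it through.** No arithmetic applies. The check is whether any passage reconciles the two instructions.

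| Source | Status of anti-emetic dexamethasone | Condition |
|---|---|---|
| 5.2, Gastrointestinal Toxicity | Allowed by name, routine use | Clinical judgement only |
| 6.6 | Barred, as a glucocorticoid | Two exceptions, below |
| Appendix 3 | Listed as prohibited | No exemption |

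1. *First exception in 6.6.* It covers symptoms of an event of clinical interest of suspected immunologic origin. Routine nausea or vomiting is not such an event.

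2. *Second exception in 6.6.* It covers physiologic doses, after consultation with the PI and Merck. Section 5.2 neither limits the dose nor asks for consultation.

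3. *Closing allowance in 6.6.* Subjects may have other medications that the investigator considers medically necessary. In context, other means outside the prohibited list, so this does not readmit dexamethasone.

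4. *Sections 5.2.1, 6.5.1 and 6.5.2.* All three allow or encourage anti-emetics in general terms. None says whether steroids are included, and none overrides 6.6. Section 6.5.1 mentions an effort to standardize supportive regimens if needed, but does not say what the standard would be.

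5. *Appendix 3.* It has to be read with the body text, because it also lists prednisone, which Table 5.4 directs for immune-related events. There, 6.6 supports the use through its first exception. For anti-emetic dexamethasone the body text contradicts itself, so reading the list alongside it does not help. The appendix marks exemptions where it intends them: topical hydrocortisone, topical or inhaled triamcinolone, and three drugs acceptable on Arm B. Dexamethasone has none. Its row gives Prozac as the trade name, an evident table error, but the drug-name column is clear.

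6. *Exclusion criterion 12 (Section 3.3.2).* It bars ongoing systemic steroid use at entry. This agrees with 6.6 and makes 5.2 the outlier.

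Result: no passage resolves the conflict.

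On size, the documents report no rate of anti-emetic steroid use, overall or by arm, and no nausea rate for vorinostat. The only nausea figure is 8%, for tamoxifen in an earlier trial (Section 1.2.3). It does not show how many patients here would receive a steroid.

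**The case against.** The best defence is that 6.6 cannot be applied literally, so specific management sections must sometimes qualify it. It bars investigational agents other than pembrolizumab, although vorinostat is itself an investigational product in Arm A. Table 5.5 lists corticosteroids for grade 3 or 4 infusion reactions, which are not among the events of clinical interest named in Sections 5.2.5.1 and 7.3.7.1. A site could reasonably read 5.2 as another specific rule that prevails. The trial also runs at a single site (Section 3.1), so practice could be settled locally, and choosing a 5-HT3 antagonist avoids the problem.

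These points stand as reasons for a low rating. They do not remove the contradiction: no text says that 5.2 prevails, Appendix 3 points the other way, and 5.2 does not tell sites to prefer the non-steroid option.

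Three stronger readings are tempting, and the documents support none of them:

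- *Use would fall mainly in Arm A.* The permission is followed by a description of vorinostat, whose "dose-limiting toxicities are anorexia, dehydration, diarrhea, and fatigue". Nausea and vomiting are not in that list, the permission names no arm, and the one nausea rate given is for tamoxifen, which is in both regimens (though it may be omitted in Arm B at the PI's discretion).
- *Steroid use would recur cycle after cycle.* Sections 5.2.1 and 6.5.2 suggest considering prophylactic anti-emetics in later cycles, but name no steroid.
- *The response comparison is biased.* Nothing in the documents shows that anti-emetic dexamethasone would change response here, or by how much.

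**Conclusion.** The inconsistency is real, and the text is wrong as written: following 5.2 gives a patient on pembrolizumab a drug that 6.6 bars, and 6.6 attaches removal from the trial to needing it. It is a low-severity fault in wording, not a disputed design choice.

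Its frequency is unknown and no effect on the primary endpoint can be quantified. The efficacy denominator does not change, because Section 8.3.1 evaluates all randomized patients. The conclusion assumes only that 5.2, 6.6 and Appendix 3 are all current text applying to the same treatment period, as they appear to be.

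**What to change.** Reword the sentence in 5.2 along these lines: *Non-steroid anti-emetics, for example 5-HT3 receptor antagonists, may be used routinely where clinically appropriate; for glucocorticoids see Section 6.6.* Deleting only the word dexamethasone would not be enough, because the permission for every anti-emetic would still include it.

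If the sponsor does intend to allow anti-emetic dexamethasone, add an explicit exception to 6.6 and Appendix 3. It should carry a dose or duration limit and an approval step, and state that such use does not trigger removal. Section 5.2 should then refer to it.

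The cost is a short protocol amendment: one sentence under the first option, a few lines under the second. Sample size and analysis are unaffected. Data collection is too, because Section 6.5.1 already requires all concomitant medication to be recorded.

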**Other Non-hematological Toxicities:**

Laboratory abnormalities must be clinically relevant, and dose and drug-related to prompt dose modifications, in case of uncertainty doses may be re-escalated if toxicities recover

Give the following dose based on the worst toxicity encountered during the previous cycle:

Fatigue	Management/Next Dose for Vorinostat
Grade 1	100%
Grade 2	Hold until toxicity is $\leq$ grade 1, then resume at dose given in prior cycle.
Grade 3, 4	Hold until toxicity is $\leq$ grade 1, then resume at 75% (or less) of dose given in the prior cycle. If grade 3 toxicity recurs despite dose reduction, decrease to 50 % of initial dose.
Other	Management/Next Dose for Vorinostat
Grade 1	100%
Grade 2	Hold until toxicity is $\leq$ grade 1, then resume at dose given in prior cycle.
Grade 3	Hold until toxicity is $\leq$ grade 1, then resume at 75% (or less) of dose given in the prior cycle. If grade 3 toxicity recurs despite dose reduction, decrease to 50 % of initial dose.
Grade 4	Discontinue protocol therapy.

**Vorinostat may be reduced for grade II fatigue, asthenia, weight loss, or other constitutional symptoms if deemed in the best interest of the patient.**

**Effects on the Eye:** Ocular disturbances, including corneal changes, decrement in color vision perception, retinal vein thrombosis, and retinopathy has been reported in patients receiving tamoxifen. An increased incidence of cataracts and the need for cataract surgery have been reported in patients receiving tamoxifen. If grade 3 or 4 ocular toxicities occur, both drugs should be stopped. Any rechallenge should be discussed with the study chair.

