#### Formulation, Appearance, Packaging, and Labeling

Vorinostat is supplied as size 3 100 mg capsules for oral administration. Vorinostat will be supplied in a 100-120 capsule bottle. Vorinostat will be given at 400 mg per day (4x 100 mg tablets), 4 of 7 days. Vorinostat is manufactured by Merck & Co., Inc.

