**Table 5.2 Arm A Regimen Description**

Investigational Product	Premedication; precautions	Dose	Route	Schedule	Cycle Length
Pembrolizumab	No premedications No precautions	200 mg	Intravenous	Day 1, Week 1 Cycles 1+	3 weeks (21 days)
Vorinostat	Administer whole with food, if possible	400 mg	Oral	Days 4 of 7 days All cycles	
Tamoxifen	No premedications No precautions	20 mg (tablets)	Oral	Daily continuous All cycles	

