## 5.2 Dose Modifications and Dosing Delays

The following dose modification rules will be used with respect to potential toxicity. Toxicity will be assessed according to the NCI CTCAE version 5.0.

The following dose modifications should be made for febrile neutropenia, and blood counts obtained on day one of each cycle. If more than one of these conditions applies, use the most stringent (i.e., the greatest dose reduction). **The AE may be due to pembrolizumab or vorinostat alone in which case the respective agent should be reduced. If overlapping toxicity is suspected, both drugs may be reduced with the potential to re-escalate the non-offending agent. Given the very different nature of pembrolizumab and vorinostat/tamoxifen toxicities, separate tables are shown for individual agents.**

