**No dose modification will be pursued for tamoxifen.**

**Hematologic Toxicity\***

**Adverse Event:\* Neutropenia**

While dose hold may apply for all days of occurrence, dose modification will only apply if neutropenia persists for day 1, 8, and 15 of each cycle. Dose modifications are not required if labs are drawn on other days and counts have recovered upon retreatment on days 1, 8, 15.

Neutropenia Febrile neutropenia	Management/Next Dose for Vorinostat
ANC $\geq$ 1000	100%
ANC: 500-1000	Hold for until $\leq$ grade 2 #, Restart at 75%: 300 mg qd for all subsequent cycles Second occurrence resume at 200 mg qd for all subsequent cycles Third occurrence: remove from study
ANC: 0-500	Hold for until $\leq$ grade 2 or less# Restart at 75%: 300 mg qd for all subsequent cycles Second occurrence resume at 200 mg qd for all subsequent cycles Third occurrence: discuss with sponsor and principal investigator, consider omitting alternate weeks

#Patient with a dose delay for more than 3 weeks in the first 2 cycles will need to be replaced for toxicity and efficacy assessments.

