**Adverse Event: Thrombocytopenia**

While dose hold may apply for all days of occurrence, dose modification will only apply if thrombocytopenia persists for day 1, 8, and 15 of each cycle. Dose modifications are not required if labs are drawn on other days and counts have recovered upon retreatment on days 1, 8, 15.

Platelets	Management/Next Dose for Vorinostat
>75'000	100 %: 400 mg qd
<75'000	100 %: 400 mg qd
$\leq$ 50'000/mm 	Hold until $\leq$ grade 2 or less Restart at 75%: 300 mg qd for all subsequent cycles Second occurrence resume at 200 mg qd for all subsequent cycles Third occurrence: discuss with sponsor and principal investigator, consider omitting alternate weeks
$\leq$ 25'000/mm 	Hold until $\leq$ grade 2 or less Restart at 75%: 300 mg qd for all subsequent cycles Second occurrence resume at 200 mg qd for all subsequent cycles Third occurrence: remove from study

An alternative to dose modification in cases of anemia only would be the use of PRBC transfusion.

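### The vorinostat step for recurrent grade 3 toxicity is tied to the starting dose, so it is no decrease at 200 mg or below, and other tables print 300 mg for a patient already at 200 mg

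*Combined protocol and SAP*

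**What the plan says.** Section 4.1.2 sets the starting dose and the unit of supply: "Vorinostat will be given at 400 mg per day (4x 100 mg tablets), 4 of 7 days" and "Vorinostat is supplied as size 3 100 mg capsules for oral administration". Table 5.2 adds "Administer whole with food, if possible".

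Section 5.2 then gives two kinds of reduction rule for vorinostat.

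- **Fatigue and Other tables** (under Other Non-hematological Toxicities). After a first grade 3 event (grade 3 or 4 for fatigue), hold and then "resume at 75% (or less) of dose given in the prior cycle". After a recurrence: "If grade 3 toxicity recurs despite dose reduction, decrease to 50 % of initial dose". A separate note lets vorinostat be lowered for grade 2 constitutional symptoms and does not say by how much.
- **Neutropenia, Thrombocytopenia, Bilirubin and AST/ALT tables.** These print fixed doses. After a first neutropenia or platelet event: "Restart at 75%: 300 mg qd for all subsequent cycles". After a second: "Second occurrence resume at 200 mg qd for all subsequent cycles". The AST/ALT table, and the bilirubin table above 3.0 mg/dl, use the same 300 and 200 mg levels by occurrence.

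Two general sentences bear on conflicts. Section 5.2 asks for the largest reduction when more than one of the listed conditions applies. Section 5.2.5 ties the adjustment to whichever system shows the worst toxicity.

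**The concern.** The two steps in the Fatigue and Other tables use different bases. The first moves with the patient's current dose; the second is fixed at half the starting dose. They form a descending sequence only if the dose in force at recurrence is above 200 mg. The other tables have the mirror-image problem: their doses depend on the occurrence count for that one toxicity and not on the dose the patient is taking.

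What is at stake is safety in Arm A. A clinician who follows the printed text after repeated toxicity could leave the dose unchanged or raise it. Section 8.2 relies on these tables for vorinostat: its six-patient check reduces only pembrolizumab, and vorinostat is left to the dose modification guidelines.

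**Working it through.** **Inputs.** Starting dose 400 mg/day and capsule strength 100 mg (Section 4.1.2); capsules given whole (Table 5.2). First grade 3 step: at most 0.75 × prior-cycle dose. Recurrence step: 0.50 × starting dose (both from the Fatigue and Other tables).

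**The plan's own levels.** 0.75 × 400 = 300 mg and 0.50 × 400 = 200 mg. These match the 300 and 200 mg printed in the AST/ALT table.

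**Fatigue and Other tables, by prior-cycle dose.** Recurrence dose = 0.50 × 400 = 200 mg in every row. Ratio = 200 ÷ dose in force at recurrence.

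| Prior-cycle dose (mg) | 0.75 × dose (mg) | Whole-capsule dose taken after first event (mg) | Recurrence dose (mg) | Ratio |
|---|---|---|---|---|
| 400 | 300 | 300 | 200 | 0.67, a true decrease |
| 400 | 300 | 200 (larger cut allowed) | 200 | 1.00, no change |
| 400 | 300 | 100 (larger cut allowed) | 200 | 2.00, conflicts with the wording |
| 300 | 225 | 200 | 200 | 1.00, no change |
| 300 | 225 | 100 (larger cut allowed) | 200 | 2.00, conflicts with the wording |
| 200 | 150 | 100 | 200 | 2.00, conflicts with the wording |

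If 225 and 150 mg could be given exactly, the ratios would be 200/225 = 0.89 and 200/150 = 1.33.

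**Can a patient be at 300 or 200 mg before the first grade 3 event?** Yes, by three routes: the fixed levels in the neutropenia, platelet, bilirubin and AST/ALT tables, the first two of which hold for all later cycles; the discretionary grade 2 reduction; or, at the first event itself, the allowance to cut by more than a quarter.

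**The other direction.** This needs no rounding and no optional cut. Grade 3 fatigue: 400 → 300 mg. Recurrence: 300 → 200 mg, as intended. The patient then has a first ANC below 1000, platelet count of 50,000 or less, AST/ALT above 2.5 × ULN, or bilirubin above 3.0 mg/dl. The relevant table prints 300 mg, and 300 ÷ 200 = 1.50, a 50% rise over the dose in force.

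**How often.** Section 1.3.1.2 reports grade 3-4 fatigue and thrombocytopenia in 2 of 34 pilot patients each (5.9%). If those rates carried over to a full Arm A of 35, 35 × 2/34 ≈ 2 patients would have each event. The faulty sequences need more than one qualifying event, or an earlier reduction plus a qualifying event, in the same patient. The documents give no frequency for such sequences.

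**The case against.** Several points against the concern are sound and narrow it.

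- **The ordinary path works.** A reader might infer that any patient already reduced gets no decrease. That is not so: a patient taken from 400 to 300 mg by these tables falls to 200 mg on recurrence.
- **No doubling is ordered.** A reader might infer that the plan tells sites to go from 100 to 200 mg. The sentence says decrease, so that reading contradicts its own wording. The accurate statement is that the instruction cannot be followed as a decrease at 200 mg or below.
- **The capsule strength does not block the first step.** Because the step allows less than 75%, 225 and 150 mg can be met with 200 and 100 mg. Only a rounding rule is missing.
- **The pilot's grade 2 rates do not show frequent reductions.** Grade 2 fatigue (27%) leads to resumption at the prior dose, with reduction optional. For platelets (grade 2 thrombocytopenia 12%), the table keeps 400 mg below 75,000 and reduces only at 50,000 or less. The hepatitis cases were immune-related and also fall under Table 5.4.
- **Effects on the comparison of arms are limited.** Section 3.1 describes a single site, so variation between sites cannot arise. Section 8.2 expects vorinostat to be adjusted individually, and Table 5.3 lets tamoxifen be omitted in Arm B, so vorinostat is not the only possible difference.

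The strongest remaining argument is that the general sentences in Sections 5.2 and 5.2.5 show an intent to keep the lower dose. The intent is plausible, but the text does not reach these cases. The Section 5.2 sentence follows a reference to febrile neutropenia and day-one blood counts and ranks conditions present together. The Section 5.2.5 sentence, once fatigue has resolved, points to the platelet or liver table and its 300 mg. The re-escalation wording covers a non-offending agent or uncertain attribution, not this sequence.

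**Conclusion.** The inconsistency is real and confined to particular sequences. The recurrence step in the Fatigue and Other tables yields no decrease at 200 mg and contradicts itself below that. The neutropenia, platelet, AST/ALT and upper bilirubin rules print a dose 50% above the one in force for a patient already at 200 mg who has a first event of that kind. This rests on the 400 mg start, on whole 100 mg capsules for the rounded rows, and on reading the general sentences as not covering successive events, which they do not expressly do.

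Few patients are likely to be affected, and the endpoint, sample size and analysis are untouched. It is a safety-relevant drafting fault of moderate priority, worth correcting because the correction is cheap.

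**What to change.** Amend Section 5.2 so that the Fatigue and Other tables, the Neutropenia, Thrombocytopenia, Bilirubin and AST/ALT tables, the general sentences in Sections 5.2 and 5.2.5, and the capsule strength in Section 4.1.2 agree. The test for the new wording is that no instruction presented as a reduction gives the same or a higher dose than the one in force. The text should also say how the tables apply when toxicities occur one after another, how a non-whole-capsule result is handled, and what happens where the recurrence step leaves no decrease. The sponsor decides the dose levels and the rules; none is proposed here.

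Cost: a wording amendment, with the usual committee and IRB approval. No added patients, visits or procedures.
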